6.18 Excluded Concomitant Medications and Procedures

The following medications and procedures are prohibited during the study.

Systemic treatment with any of the following metabolizing enzyme inducers should be avoided, unless there is no appropriate alternative medication for the patient's use:

- Strong CYP3A inducers: rifampin, rifapentine, rifabutin, carbamazepine, phenytoin, and phenobarbital
- Excluded foods and dietary supplements include St. John's wort.

6.19 Permitted Concomitant Medications and Procedures

The following medications and procedures are permitted during the study:

- Antiemetics, including 5-HT₃ serotonin receptor antagonists, may be used at the discretion of the investigator.
- Loperamide or other antidiarrheal should be used for symptomatic diarrhea at discretion of the investigator. The dose and regimen will be according to institutional guidelines. fluid replacement should be given to prevent volume depletion.
- Antiviral therapy (in addition to the patient's antiretroviral regimen) such as acyclovir may be administered if medically appropriate.
- Supportive measures consistent with optimal patient care may be given throughout the study.

6.20 Precautions and Restrictions

Fluid deficit should be corrected before initiation of treatment and during ixazomib treatment. Nonsteroidal anti-inflammatory drugs (NSAIDs) should be avoided with impaired renal function given reported NSAID-induced renal failure in patients with decreased renal function.

The NNRTIs etravirine and efavirenz are moderate CYP3A4 enzyme inducers and have potential to decrease systemic exposure to ixazomib. That possibility will be explored by measuring ixazomib levels in all patients and comparing ixazomib concentrations in patients on different ART regimens.

Pregnancy

It is not known what effects ixazomib has on human pregnancy or development of the embryo or fetus. Therefore, female patients participating in this study should avoid becoming pregnant, and male patients should avoid impregnating a female partner. Male patients should use effective methods of contraception through defined periods during and after study treatment as specified below.

Female patients must meet 1 of the following:

Postmenopausal for at least 1 year before the screening visit, or surgically sterile.

Regardless of above criteria, females must have a negative urine pregnancy test prior to receiving the 1st dose of ixazomib.

Male patients, even if surgically sterilized (ie, status postvasectomy) must agree to 1 of the following:

- Practice effective barrier contraception AND a second method of contraception for female partners of childbearing potential during the entire study treatment period and through 90 days after the last dose of ixazomib, or
- Agree to practice true abstinence, when this is in line with the preferred and usual lifestyle of the subject. (Periodic abstinence [eg, calendar, ovulation, symptothermal, postovulation methods for the female partner] and withdrawal are not acceptable methods of contraception.)
- AND
- Agree to forego sperm donation for the same period as above.

6.21 Management of Clinical Events

Adverse drug reactions such as thrombocytopenia, diarrhea, fatigue, nausea, vomiting, and rash have been associated with ixazomib treatment. Management guidelines regarding these events are outlined below. Further details of management of ixazomib AEs are described in the ixazomib IB.

Prophylaxis Against Risk of Reactivation of Herpes Infection

Patients may be at an increased risk of infection including reactivation of herpes zoster and herpes simplex viruses. Antiviral therapy such as acyclovir, valacyclovir, or other antivirals may be initiated as clinically indicated.

Nausea and/or Vomiting

Standard anti-emetics including 5-hydroxytryptamine 3 serotonin receptor antagonists are recommended for emesis if it occurs once treatment is initiated; prophylactic anti-emetics may also be considered at the physician's discretion. Fluid deficit should be corrected before the patient takes ixazomib.

Diarrhea

Prophylactic antidiarrheals will not be used in this protocol. However, diarrhea should be managed according to clinical practice, including the administration of antidiarrheals once infectious causes are excluded. Fluid intake should be maintained to avoid dehydration. Fluid deficit should be corrected before the patient takes ixazomib.

Erythematous Rash With or Without Pruritus

As with bortezomib, rash with or without pruritus has been reported with ixazomib, primarily at the higher doses tested and when given with agents where rash is an overlapping toxicity. The rash may range from limited erythematous areas, macular and/or small papular bumps that may or may not be pruritic over a few areas of the body, to a more generalized eruption that is predominately on the trunk or extremities. Rash has been most commonly characterized as maculopapular or macular. To date, when it does occur, rash is most commonly reported within the first 3 cycles of therapy. The rash is often transient, self-limiting, and is typically Grade 1 to 2 in severity.

Symptomatic measures such as antihistamines or corticosteroids (oral or topical) have been successfully used to manage rash and have been used prophylactically in subsequent cycles. The use of a topical, IV, or oral steroid (eg, prednisone \leq 10 mg per day or equivalent) is permitted. Management of a Grade 3 rash may require intravenous antihistamines or corticosteroids. Administration of ixazomib (and/or other causative agent if given in combination) should be modified per protocol and re-initiated at a reduced level from where rash was noted (also, per protocol).

In line with clinical practice, dermatology consult and biopsy of Grade 3 or higher rash or any SAE involving rash is recommended. Prophylactic measures should also be considered if a patient has previously developed a rash (eg, using a thick, alcohol-free emollient cream on dry areas of the body or oral or topical antihistamines). The rare risks of Stevens-Johnson syndrome, TEN, DRESS syndrome and pemphigus vulgaris have been reported in oncology studies when ixazomib (or placebo) has been given in a multi-drug regimen, with concomitant medications known to cause rash, and/or in the setting of confounding treatment emergent adverse events. These severe, potentially life-threatening, or deadly conditions may involve rash with skin peeling and mouth sores and should be clinically managed according to standard medical practice. Study medication should be discontinued in the event of severe, potentially life-threatening rash. Punch biopsies for histopathological analysis are encouraged at the discretion of the investigator.

Thrombocytopenia and anemia

Blood counts should be monitored regularly as outlined in the protocol with additional testing obtained according to standard clinical practice. Thrombocytopenia has been seen in patients with cancer and patients that were treated with combination anti-cancer therapy which included ixazomib, and may be severe but has been manageable with platelet transfusions according to standard clinical practice. Ixazomib administration should be modified as noted as

per dose modification recommendations in the protocol when thrombocytopenia occurs (See Page 39 above). Therapy can be reinitiated at a reduced level upon recovery of platelet counts. A rare risk is thrombotic thrombocytopenic purpura (TTP), a rare blood disorder where blood clots form in small blood vessels throughout the body characterized by thrombocytopenia, petechiae, fever, or possibly more serious signs and symptoms. TTP should be managed symptomatically according to standard medical practice. Red blood cell transfusions should be administered for the treatment of anemia according to standard clinical practice.

Neutropenia

Blood counts should be monitored regularly as outlined in the protocol with additional testing obtained according to standard clinical practice. Neutropenia may be severe but has been manageable. Ixazomib administration should be modified as noted as per dose modification recommendations in the protocol when neutropenia occurs (see Page 39 above). Therapy can be reinitiated at a reduced level upon recovery of ANCs.

Fluid Deficit

Dehydration should be avoided since ixazomib may cause vomiting, diarrhea, and dehydration. Acute renal failure has been reported in patients treated with ixazomib, commonly in the setting of the previously noted gastrointestinal toxicities and dehydration.

Fluid deficit should be corrected before initiation of ixazomib and as needed during treatment to avoid dehydration.

Hypotension

Symptomatic hypotension and orthostatic hypotension with or without syncope have been reported with ixazomib. Blood pressure should be closely monitored while the patient is on study treatment and fluid deficit should be corrected as needed, especially in the setting of concomitant symptoms such as nausea, vomiting, diarrhea, or anorexia. Patients taking medications and/or diuretics to manage their blood pressure (for either hypo- or hypertension) should be managed according to standard clinical practice, including considerations for dose adjustments of their concomitant medications during the course of the trial. Fluid deficit should be corrected before initiation of ixazomib and as needed during treatment to avoid dehydration.

Posterior Reversible Encephalopathy Syndrome

One case of posterior reversible encephalopathy syndrome, which ultimately resolved, has been reported with ixazomib. This condition is characterized by headache, seizures and visual loss, as well as abrupt increase in blood pressure. Diagnosis may be confirmed by

magnetic resonance imaging (MRI). If the syndrome is diagnosed or suspected, symptom-directed treatment should be maintained until the condition is reversed by control of hypertension or other instigating factors.

Transverse Myelitis

Transverse myelitis has also been reported with ixazomib. It is not known if ixazomib causes transverse myelitis; however, because it happened to a patient receiving ixazomib, the possibility that ixazomib may have contributed to transverse myelitis cannot be excluded.

7 Statistical Plan

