4.4 Early Withdrawal of Subjects

4.4.1 When and How to Withdraw Subjects

Permanently discontinue ixazomib in individual subjects if any of the following occur:

- Death of any subject
- Anaphylactic reaction in any subject
- A life-threatening adverse event in any subject
- Any Grade 3 AE (except if there is clear evidence that it is not study drug related – i.e. a plausible alternative reason).
- Any Grade 4 AE
- A decrease in CD4 count below 350 cells/mm³, confirmed on repeat testing within 2 weeks, and associated with a relative drop in CD4 T cell percentage by >25% from baseline values, in the absence of an alternative explanation
- Confirmed virologic rebound (HIV-1 RNA >500 copies/ml confirmed by a second assay done within 14 days of the initial one). If the HIV-1 viral load is >20 copies/mL and <500 copies/mL, the HIV-1 viral load will be rechecked every 2 weeks until it becomes <20 copies/mL or >500 copies/mL.
- Development of \geq Grade 1 peripheral neuropathy with or without pain

An independent Data Safety and Monitoring Board will review the case. The committee and principal investigators will determine whether there is an association between the event and the ixazomib. The DSMB will make a recommendation accordingly as to whether the study should proceed, or if a modification in trial design is required, or if a replacement subject should be enrolled at the same dose as the withdrawn subject.

Reasons for early withdrawal of individual subjects may include:

- Subjects refuse to return for any remaining study visits.
- Subjects discontinue the ixazomib at any time during the study.
- Safety reasons, either at the discretion of the Investigator or at the subject's request.
- Protocol violations at the discretion of the principal investigators.
- Initiation of concomitant therapy that could interfere with the results of the study or ixazomib
- Subject's decision to withdraw, at any time.

All subjects are free to withdraw from participating in this study at any time and for whatever reason, specified or unspecified, and without prejudice.

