	≥Grade 2 increase in AST, ALT or total bilirubin	Ixazomib	Ixazomib dose should be omitted until the abnormal LFT has recovered to baseline values. Ixazomib may be reinitiated at the same dose if the recovery has occurred in less than 7days. If the abnormality lasts ≥7 days or recurs, then the dose of ixazomib should be reduced by one dose level. If a patient is already at the lowest dose level, ixazomib should be permanently discontinued. Patients should have LFTs checked weekly until resolution of abnormality.
Skin and subcutaneous tissue disorders	Any Grade ≤2 Rash	Ixazomib	Omit ixazomib until rash resolves. Restart at same dose. If the rash recurs, reduce dose by one dose level. If a patient is already at the lowest ixazomib dose, ixazomib should be permanently discontinued.
	Any rash, ≥Grade 3	Ixazomib	Ixazomib should be permanently discontinued.

CTCAE System/Organ/Class (SOC)	ADVERSE EVENT	AGENT	ACTION**
Nervous System Disorders	Grade 1 peripheral neuropathy	Ixazomib	Ixazomib should be permanently discontinued.
Other	Any Grade 3 AE (except if there is clear evidence that it is not ixazomib related – i.e. a plausible alternative reason).	Ixazomib	Permanently discontinue ixazomib.
	Grade 4 AE	Ixazomib	Permanently discontinue ixazomib
	Plasma HIV RNA >500copies/ml on 2 consecutive occasions. (except if there is clear evidence that it is not ixazomib related – i.e. a plausible alternative reason – for example missed ART doses).	Ixazomib	Permanently discontinue ixazomib. Perform HIV genotypic resistance testing.

Use the NCI Common Terminology Criteria for Adverse Events (CTCAE) version 4.0* unless otherwise specified for all Adverse Events.

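### The rash text in Section 6.21 calls for restart at a reduced level, while Section 6.17 Table 2 stops ixazomib permanently for any rash of Grade 3 or higher

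*Combined protocol and SAP*

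**What the plan says.** Three places give rules for ixazomib after a rash.

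- **Section 6.21, erythematous rash text.** One sentence covers treatment of Grade 3 rash: "Management of a Grade 3 rash may require intravenous antihistamines or corticosteroids". The next says that administration of ixazomib "should be modified per protocol and re-initiated at a reduced level from where rash was noted (also, per protocol". That sentence names no grade and does not separate a first rash from a recurrence. Later, after the rare serious skin reactions, the text adds: "Study medication should be discontinued in the event of severe, potentially life-threatening rash".
- **Section 6.17 Table 2, rash rows.** For rash of Grade 2 or lower: "Omit ixazomib until rash resolves. Restart at same dose. If the rash recurs, reduce dose by one dose level". A patient already at the lowest dose stops permanently. The second row, "Any rash, ≥Grade 3", requires permanent discontinuation and has no exception for cause.
- **Section 4.4.1.** Ixazomib is permanently discontinued for, among other events, "Any Grade 3 AE (except if there is clear evidence that it is not study drug related" and so on, the exception being a plausible other cause.

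**The concern.** A clinician managing a rash would naturally turn to the rash guidance in Section 6.21. Taken alone, it gives a higher threshold for stopping than Table 2 does. A Grade 3 rash that is not life-threatening appears there as something to treat, followed by restart at a lower dose. Table 2 and Section 4.4.1 would have ended dosing.

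What is at stake is re-exposure to the drug after a Grade 3 rash. Section 1.5 describes the participants as otherwise healthy and unlikely to benefit directly. A protocol with two written answers to the same dosing question also makes it unclear which action is a deviation.

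**Working it through.** The protocol states no figure on this point and no arithmetic applies. The check sets the two sections side by side, scenario by scenario.

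| Scenario | Section 6.17 Table 2 | Section 6.21 rash text | Agree? |
|---|---|---|---|
| First rash, Grade 2 or lower | Hold, then same dose | Reduced level, if the sentence covers all grades | No, on that reading |
| Recurrent rash, Grade 2 or lower, above the lowest dose | Hold, then one level down | Reduced level, on the same reading | Yes |
| Recurrent rash, Grade 2 or lower, at the lowest dose | Stop permanently | Reduced level, on the same reading, but none is defined | No, on that reading |
| Grade 3, not life-threatening | Stop permanently | Reduced level | No |
| Severe, potentially life-threatening | Stop permanently | Stop | Yes |

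**Step 1: which grades does the restart sentence cover?** Its position directly after the Grade 3 sentence supports a Grade 3 reading. The lack of any grade limit supports an all-grades reading. So does the scope of the subsection, which says of rash in general: "The rash is often transient, self-limiting, and is typically Grade 1 to 2 in severity".

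**Step 2: test each reading.** Read as Grade 3 only, the sentence contradicts the Grade 3 row of Table 2. It also contradicts Section 4.4.1 unless the rash is clearly unrelated to drug. Read as all grades, it contradicts those and the first-rash rule as well. At the lowest dose it cannot be carried out, because the dose groups go no lower than 1 mg. The only reading without conflict confines the sentence to recurrent mild rash above the lowest dose, and nothing in Section 6.21 confines it that way.

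**Step 3: do the two references to the protocol resolve it?** They point the reader to the dosing rules, but the sentence still names an outcome. Among the rash rules, Table 2 gives restart at a reduced level only for recurrent rash of Grade 2 or lower. A reader who follows the reference for a Grade 3 rash finds no reduced-level restart there.

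**Step 4: does the stop sentence in Section 6.21 already cover Grade 3?** It joins severe with potentially life-threatening and follows the list of rare, dangerous skin conditions, so it most naturally means those. If severe were taken to mean Grade 3, Section 6.21 would contradict its own restart sentence.

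**The case against.** The strongest reply is that Table 2 governs. The restart sentence defers to the protocol twice. Section 6.21 presents itself as management guidance, and the sentence mentions other agents given in combination, which suggests general text carried over from elsewhere. Table 2 is the graded set of instructions to apply before each dose, and Section 5.4 requires all protocol criteria for administration to be met and documented first. Section 4.4.1, the dose-limiting toxicity list in Section 6 and the stopping rules in Section 9.3 also act on Grade 3 events not clearly unrelated to drug, with DSMB review. This stands as an argument about likely practice, and it keeps the severity low. It does not remove the contradiction in the text.

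It is also fair to object that the first-rash conflict depends on the all-grades reading. That stands, and the point on first rash is conditional on it.

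A reader might go further and infer that dose escalation is at risk. On that view, a patient reduced after a mild rash in Cycle 1 could count among the three patients without dose-limiting toxicity while receiving less than the cohort dose. The documents do not support a claim of that kind:

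- It needs the all-grades reading, and a rash early enough to change later Cycle 1 doses. Section 6.21 says only that "rash is most commonly reported within the first 3 cycles of therapy", so a Cycle 1 rate cannot be derived.
- The rash rate of about 50% in Section 1.4 is an overall figure, higher in combination with lenalidomide. It is not a rate for this regimen or for Cycle 1.
- Table 2 itself omits drug until the rash resolves. A rash that leads to one omitted dose already removes one of the three Cycle 1 doses under the correct rule. A lowered Cycle 1 dose is therefore not specific to this conflict.
- A Grade 3 rash not clearly unrelated to ixazomib is a dose-limiting toxicity whether or not drug is restarted. The Grade 3 conflict therefore leaves the escalation decision unchanged.

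**Conclusion.** The contradiction is real and the sentence is wrong as written. On the narrow reading, one Table 2 rash action is contradicted: permanent discontinuation for a Grade 3 rash that is not life-threatening. On the all-grades reading, the same-dose restart after a first rash of Grade 2 or lower is contradicted too, and the instruction has nothing to apply to at the lowest dose.

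Severity is minor. That judgement assumes that sites apply Table 2 as the dosing rule and that Grade 3 events reach the DSMB as planned. The documents give no Grade 3 rash rate, so no expected number of affected participants can be stated. No sample size, endpoint or analysis depends on the point.

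A reader might also infer a parallel conflict in the platelet and neutrophil sentences of Section 6.21. There is none. Those sentences permit a reduced-level restart rather than direct it, defer to the dose rules, and fit the Table 2 row for Grade 2 counts that last at least 7 days or recur. Their pointer to page 39, where the contents list puts Table 2 on page 53, is an editorial matter only.

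**What to change.** Replace the restart sentence in the Section 6.21 rash text with:

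> Ixazomib holds, restarts and reductions for rash follow Section 6.17 Table 2. First rash of Grade 2 or lower: hold until resolved and restart at the same dose. Recurrence: reduce one dose level, or discontinue permanently if already at the lowest dose. Any rash of Grade 3 or higher: discontinue permanently and do not restart.

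This restates rules already in Table 2 and introduces no new ones. The advice on treating Grade 3 rash can stay, since it concerns symptoms and not dosing. The platelet and neutrophil sentences need no substantive change. The page 39 pointers can be corrected at the same time as a matter of editing.

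The cost is one sentence in an amendment, with no change to sample size, visits or analyses.

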7.1 Sample Size Determination

For this Phase I/II single-center study, the sample size is primarily determined by the estimated number of patients that can be successfully recruited during the study time period.

7.2 Statistical Methods

Descriptive Statistics

Univariate descriptive statistics and frequency distributions will be calculated, as appropriate for all variables. Baseline values for demographic, clinical, and outcome variables will be tabulated for the treatment groups. These analyses will help identify potential confounding variables to be used as covariates in sensitivity analyses. Putative prognostic variables that will be investigated through these descriptive analyses include variables such as age, sex, race/ethnicity, and duration of HIV infection, baseline CD4 T cell count and HIV viral load, mode of transmission, duration of ART, and duration of viral suppression.

Multiplicity

No *a priori* correction to the type I error rate is warranted for this study.

Primary Analysis

Ixazomib will be safe and well tolerated in HIV positive persons on suppressive ART.

Description statistics will be used to describe the rates of adverse effects by CTC grade of ixazomib among the dosing groups.

Secondary Analysis 1:

Ixazomib will reduce HIV DNA and replication competent viral reservoir size and improve CD4 T cell counts in HIV positive patients on suppressive ART.

To test this hypothesis, a mixed model will be estimated for each outcome separately. This model will consider linear trajectories and more flexible distribution of outcomes over time using each assessment point as a factor (i.e., a “repeated measures ANOVA formulation”). Given the limitations of the sample size, random effects for only subject (random intercept) models will be considered. These models will examine the treatment by time interaction and the linear trajectory model will be expected to have greater, but relatively poor, power to detect differences in outcomes such as viral load over time. An alpha of 0.1 or lower will be considered sufficiently significant to serve as preliminary evidence of a biologic effect to warrant further studies.

In the event the models are not able to be estimated from the data available, a planned post-hoc analysis will compare changes in secondary endpoints between participants on integrase inhibitor-based ART and non-nucleoside reverse transcriptase-based ART.

Interim Analysis

There is no interim analysis in this protocol, each cohort/dose level will be reviewed by the DSMB and decide upon escalation to the next dose level. This review will be conducted when all treated patients/cohort have received 4 weeks of treatment, or earlier if a DLT has occurred. Thereafter DSMB will review each cohort monthly.

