4.3 Subject Recruitment, Enrollment and Screening

A maximum total of 17 subjects will be recruited from patients from the Mayo Clinic HIV Clinic and the Hennepin County Medical Center (HCMC). Potential study subjects will be identified and screened for inclusion and exclusion criteria by a member of the study team. Furthermore, other treating clinicians, including residents, fellows and staff physicians, in the Mayo Clinic HIV clinic and HCMC continuity clinic may refer potential study subjects to a study team member. Evaluation and documentation of inclusion and exclusion criteria will be obtained and recorded by an investigator prior to enrollment. Informed consent will be obtained by an MD investigator. Patients will be remunerated for participation in the study (see section 12.3).

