5.2 Treatment Regimen

Patients will be treated in sequential groups after the safety evaluation of each group by the DSMB. Visits 1 and 2 do not have a time window, and can occur without DSMB review as patients will not receive drug at those visits. The following groups will be studied in this protocol:

Group 1: 3 patients with HIV infection, who meet inclusion criteria, will receive ixazomib 1 mg on days 1, 8 and 15 for 28 days. After 28 days, the DSMB will meet to decide if enrollment of the next cohort should proceed. After 84 days (28 days x 3 cycles), the DSMB will meet and decide if patients will receive either (i) ixazomib once weekly for 12 weeks or (ii) ixazomib 1 mg on days 1, 8 and 15 for an additional three 28 days cycles. Visits 3-15 will have a window of \pm 3 days.

Group 2: 3 patients with HIV infection, who meet inclusion criteria, will receive ixazomib 2 mg on days 1, 8 and 15 for 28 days. After 28 days, the DSMB will meet to decide if enrollment of the next cohort should proceed. After 84 days (28 days x 3 cycles), the DSMB will meet and decide if patients will receive either (i) ixazomib once weekly for 12 weeks or (ii) ixazomib 2 mg

on days 1, 8 and 15 for an additional three 28 days cycles. Visits 3-15 will have a window of ± 3 days.

[figure not shown]
Group 3: 3 patients with HIV infection, who meet inclusion criteria, will receive ixazomib 3 mg on days 1, 8 and 15 for 28 days. After 28 days, the DSMB will meet to decide if enrollment of the next cohort should proceed. After 84 days (28 days x 3 cycles), the DSMB will meet and decide if patients will receive either (i) ixazomib once weekly for 12 weeks or (ii) ixazomib 3 mg on days 1, 8 and 15 for an additional three 28 days cycles. Visits 3-15 will have a window of ± 3 days.

Group 4: 3 patients with HIV infection, who meet inclusion criteria, will receive ixazomib 4 mg on days 1, 8 and 15 for 28 days. After 28 days, the DSMB will meet to decide if enrollment of the next cohort should proceed. After 84 days (28 days x 3 cycles), the DSMB will meet and decide if patients will receive either (i) ixazomib once weekly for 12 weeks or (ii) ixazomib 4 mg on days 1, 8 and 15 for an additional three 28 days cycles. Visits 3-15 will have a window of ± 3 days.

Group 5: 5 patients with HIV infection, who meet inclusion criteria will receive the maximum tolerated dose of ixazomib as determined by DSMB recommendation. Visits 3-15 will have a window of ± 3 days.

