5.3 Method for Assigning Subjects to Treatment Groups

Each group (or dose level) will enroll and after 4 weeks of follow up of 3 patients treated with ixazomib at a particular dose will be reviewed for safety by DSMB before initiating enrollment into the next group (or dose level). All patients in the current cohort must have completed 4 weeks and the cohort's data reviewed by the by the Safety Monitoring Committee before patients in the next cohort can receive drug. Patients from the next cohort may complete the first two visits prior to DSMB review of earlier cohorts.

Dose limiting toxicities are defined in Section 6.17 Table 2. After all the subjects in each dosing group has completed Cycle 1 of ixazomib, the DSMB may recommend:

- (i) Proceed to next dose level, or
- (ii) Terminate trial, or
- (iii) Enroll a replacement subject for a withdrawn subject, or
- (iv) Add 5 more patients at previous dose group (maximum tolerated dose). The maximum tolerated dose is that level where no more than 0 out of 3 patients experience dose limiting toxicity.

If no DLT are observed in 3 subjects, the next dosing level will be initiated.

After DSMB review of the 4 mg dosing level, if no DLT are observed, the DSMB may recommend:

- (i) Terminating the trial
- (ii) Enroll 5 more patients at the maximum tolerated dose.

The NNRTIs etravirine and efavirenz are moderate CYP3A enzyme inducers and have potential to decrease systemic exposure to ixazomib. That possibility will be explored by measuring trough ixazomib levels in all patients and comparing ixazomib concentrations in patients on different ART regimens. The DSMB will have to consider the number of patients treated with NNRTIs in a particular group as the safety profile of a group may be underestimated if the majority of patients are treated with NNRTIs as part of their ARV regimen.

Additional data review by the DSMB will occur after Day 84 for each dosing cohort. At this time, the DSMB may recommend:

[figure not shown]
- (i) Proceed to uninterrupted weekly dosing on days 1, 8, 15 and 22 of a 28 day cycle, or
- (ii) Continue previous dosing on days 1, 8, and 15 of a 28 day cycle, or
- (iii) Enroll a replacement subject for a withdrawn subject, or
- (iv) Terminate dosing.

This determination will be made on an individual participant basis, and not a dosing cohort basis, and will be made based on the presence or absence of adverse drug effects that do not meet the definition of dose related toxicities.

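### The primary safety analysis in section 7.2 carries no measure of uncertainty, although zero events in 3 to 8 patients would leave DLT rates of 31% to 63% open

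*Combined protocol and SAP*

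**What the plan says.** Under Primary Analysis, section 7.2 gives two sentences. The first is the hypothesis: "Ixazomib will be safe and well tolerated in HIV positive persons on suppressive ART". The second is the method: "Description statistics will be used to describe the rates of adverse effects by CTC grade of ixazomib among the dosing groups". By contrast, Secondary Analysis 1 in the same section also opens with an assertion but follows it with a model and an alpha of 0.1.

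The denominators come from sections 5.2 and 5.3. Each of four escalation groups has 3 patients; for the first, "Group 1: 3 patients with HIV infection, who meet inclusion criteria, will receive ixazomib 1 mg on days 1, 8 and 15 for 28 days". Escalation works on zero counts: "If no DLT are observed in 3 subjects, the next dosing level will be initiated". So does dose selection: "The maximum tolerated dose is that level where no more than 0 out of 3 patients experience dose limiting toxicity". The DSMB may then recommend to "Enroll 5 more patients at the maximum tolerated dose". Section 4.3 caps the total: "A maximum total of 17 subjects will be recruited from patients".

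Section 7.1 sets no precision target; "the sample size is primarily determined by the estimated number of patients that can be successfully recruited during the study time period". Section 7.3 bases the primary analysis on everyone who received at least one dose. Section 6 counts three things as DLTs: any Grade 4 or higher toxicity, any Grade 3 event unless clearly unrelated, and any peripheral neuropathy of Grade 1 or higher.

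**The concern.** A hypothesis of safety cannot be assessed from point rates alone when the denominators are 3, 5 or 8. An observed rate of 0% in such a group looks reassuring, but the number of patients sets how much it excludes, and the plan never asks for that to be shown. The secondary question has a stated evidential standard and the primary one has none.

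The result will be used. Section 1.5 says the maximum tolerated dose is meant to inform the design of later studies, and section 7.3 looks ahead to a Phase II/III confirmatory study. Sections 1.4 and 1.5 report no published experience in HIV-positive people and no healthy-volunteer data, and expect no direct benefit for participants. A rate passed on without its bound would carry more certainty than the data hold.

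**Working it through.** **Inputs.** 3 patients per escalation dose (section 5.2); 5 more at the selected dose (sections 5.2 and 5.3); maximum of 17 (section 4.3). The documents give no confidence level for the primary analysis. I assume one-sided 95% and show two alternatives.

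**The plan's own figure.** 4 × 3 + 5 = 17, which matches. Section 7.1 has no statistical formula to reproduce. A result of 0/17 can arise only if all four doses are cleared and the expansion is at 4 mg.

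**Upper bound after zero events.** The exact (Clopper-Pearson) bound is 1 − a^(1/n), with a = 0.05 (one-sided 95%), 0.025 (two-sided 95%) or 0.10 (one-sided 90%). For n = 3, 1 − 0.05^(1/3) = 0.632.

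| Result | One-sided 95% | Two-sided 95% | One-sided 90% |
|---|---|---|---|
| 0/3 (one dose group) | 63.2% | 70.8% | 53.6% |
| 0/5 (expansion alone) | 45.1% | 52.2% | 36.9% |
| 0/8 (3 + 5 at the selected dose) | 31.2% | 36.9% | 25.0% |
| 0/17 (all doses pooled) | 16.2% | 19.5% | 12.7% |

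With one event in 8, the one-sided 95% bound rises to 47.1% (the 0.95 quantile of a beta distribution with parameters 2 and 7).

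**Chance of a clean result.** P(0 of n) = (1 − p)^n.

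- True rate 20%: 0.8^3 = 51.2% for 0/3 and 0.8^8 = 16.8% for 0/8.
- True rate 30%: 0.7^3 = 34.3% for 0/3 and 0.7^8 = 5.8% for 0/8.

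**Effect of selecting the dose on 0/3.** The ordinary 0/8 bound assumes that the first 3 results were free to vary. At the selected dose they were not, because the dose qualifies by showing 0/3. At a true rate of 31.2%, the unconditional chance of 0/8 is 0.688^8 = 5%. Given that the first 3 are already clean, it is 0.688^5 = 15%. So a statement that 0/8 excludes rates above 31% at 95% confidence would be too strong. The 15% applies in full if DLTs are counted over the same period as the selecting review. That review is at 4 weeks (section 5.3) and treatment lasts 24 weeks, so for events over the whole course the figure lies between 5% and 15%. The 5 expansion patients enter after selection, and their bound of 45% is not affected.

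**The case against.** A reader might infer that a clean table of 3 patients will be declared proof of safety, or that no result could count against the hypothesis. The documents support neither. They contain no rule for declaring safety, and the primary paragraph plans description, not a test. Single events do have consequences: one DLT means a dose level fails the 0/3 definition, and section 9.3 sends a death, any Grade 4 event, any Grade 3 event not clearly unrelated, a CD4 fall below 350 or confirmed viral rebound to committee review. These points stand.

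The 0/3 criterion is an escalation and dose-selection rule, not the primary analysis, and it does not act alone. At an illustrative constant rate of 20%, four clean cohorts in a row have probability 0.8^12 = 6.9%, far below the 51% for one cohort. That also stands, so the 63% figure should not be read as the trial's overall safety statement.

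A DLT here is not the same as serious harm. It includes Grade 1 neuropathy, which Appendix I describes as asymptomatic. Failing to exclude a DLT in about one participant in three is therefore weaker than failing to exclude serious toxicity at that rate.

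Finally, descriptive safety reporting is usual in a pilot, a reader can compute bounds from the counts, and the DSMB charter's analysis plan (section 9.4.1) is not among the supplied documents and may contain more. These points limit the importance of the concern without answering it. The charter serves monitoring, whereas section 7.2 governs the final analysis, and there the hypothesis stands without a measure of uncertainty.

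**Conclusion.** The concern holds as a limit on the final primary analysis. Section 7.2 pairs an unqualified safety hypothesis with rates that carry no measure of uncertainty. With zero events, the one-sided 95% bounds are 63% for a dose group of 3, 45% for the 5 expansion patients and 31% for the 8 at the selected dose, the last subject to the selection caveat. The conclusion does not depend on the confidence level: even at one-sided 90%, 0/8 leaves rates up to 25% open.

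The figures assume independent patients, a common rate within each dose and no replacement subjects, whom section 5.3 allows and who would change the denominators. The 0/8 figure also assumes that the 3 escalation and 5 expansion patients are combined, which section 7.2 does not state. The finding supports no criticism of trial conduct or participant protection. It is an inexpensive improvement to what the trial can conclude.

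**What to change.** In section 7.2:

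- Reword the primary aim as estimating the rates of toxicity.
- Report, by dose and at the selected dose, the proportion of treated participants with at least one DLT and with at least one Grade 3 or higher adverse event. Give each an exact (Clopper-Pearson) upper bound at a stated confidence level.
- At the selected dose, show the expansion patients alone (0/5 would give 45%) as the bound unaffected by selection. Show the combined 3 + 5 (0/8 would give 31%) labelled as including the patients whose clean result selected the dose.
- Label any pooled figure (0/17 would give 16%) as mixing 1 to 4 mg, and do not use it to describe the selected dose.
- Report DLTs that are Grade 1 neuropathy separately from Grade 3 or higher events.
- Word any safety conclusion with the rate that the bound excludes.

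The cost is a few sentences, one table column and a visibly less favourable safety statement. Sample size, doses, escalation and stopping rules are unchanged.
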